4.1 Assignment of interventions

The subjects will be randomized into one of six possible randomization orders (Table 4).

Table 4. Randomization orders

1.	2.	3.	4.	5.	6.
Mattress A	Mattress A	Mattress B	Mattress B	Mattress C	Mattress C
Mattress B	Mattress C	Mattress A	Mattress C	Mattress A	Mattress B
Mattress C	Mattress B	Mattress C	Mattress A	Mattress B	Mattress A

A = Alternating Low Pressure mattress with low air loss function (IsoAir, stryker, USA)

B = Reactive support surface, gel mattress (IsoGel, stryker, USA)

C = Standard mattress (basic foam)

4.2 Allocation concealment

Sequentially numbered opaque sealed envelopes containing the group assignment will be prepared and used. Envelope preparation will be done by the data manager of the CRC who is not involved in any study preparation or procedures at this stage.

4.3 Allocation implementation

The batch of sequentially numbered envelopes is stored at the CRC. Envelopes are opened after confirming eligibility and provision of informed consent.

4.4 Blinding

Due to the nature of the intervention study assistants and researchers will not be blinded.

The data manager and statistician will be blinded.

5 Methods: data collection, management, analysis

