3.2 Interventions

After giving informed consent and checking the in- and exclusion criteria, the subjects will be randomized into three study groups (three different support surfaces):

- (1) Alternating Low Pressure mattress with low air loss function (IsoAir, stryker, USA)
- (2) Reactive support surface, gel mattress (IsoGel, stryker, USA)
- (3) Standard mattress (basic foam)

The support surfaces will be used according to the manufacturer instructions. Every subject will lie on every mattress. Therefore, every subject will have at least three visits in the study center of approximately 4 hours. The order of mattress use will be randomized for the visits.

The study volunteers will be requested, to acclimatize for 30 min at 40-60% relative humidity and a temperature of 20-22°C with having the right lateral heel, sacral and sternal skin uncovered. During this time the right lateral heel skin, the sacral and sternal skin will be marked in prone position. Once in prone position the baseline skin measurements on the right lateral heel and sacral skin will be conducted (order see below: Sequence of measurements), that no/minimal interferences between measurements occur (Kottner et al. 2014). After that, the participants will stay in supine position for two hours. The baseline sternal skin measurements will be performed immediately after the subjects turned into supine position. At the end of two hours the sternal skin measurements will be repeated. After two hours, the subjects turn into prone position again and the skin measurements on the right lateral heel and sacral skin will be conducted again to capture the effect of the two hour loading on the mattress. The measurements will be repeated after 20 min to observe the adjustments after offloading. Study procedures and measurements will be conducted always and only in the morning to minimize possible circadian influences. The procedures will be performed on all visits in the same way and order, only the support surface will change.

Sequence of measurements:

- (1) TEWL
- (2) Skin surface temperature
- (3) Stratum corneum hydration (SCH)
- (4) Erythema
- (5) Epidermal and dermal hydration
- (6) Skin elasticity
- (7) Skin roughness
- (8) Taking of OCT images (only for standard mattress (basic foam))

Measurements will be performed two times per measurement area. Every value will be recorded separately.

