3.3 Outcomes and variables

Because this is an exploratory study, no distinction will be made between primary and secondary outcomes.

Table 1. Outcomes

Name	Method and metric	Time points of data collection
TEWL	
 · Tewameter TM 300 (Courage + Khazaka, Cologne, Germany) · Means of duplicate measurements per skin area in g/m²/h 	BL, after 2 hours and 20 minutes after loading
Erythema	
 · Mexameter MX 18 · Means of duplicate measurements per skin area in arbitrary units 	BL, after 2 hours and 20 minutes after loading
SCH	
 · Corneometer CM 825 (Courage + Khazaka, Cologne, Germany) · Means of duplicate measurements per skin area in arbitrary units 	BL, after 2 hours and 20 minutes after loading
Skin roughness	
 · Visioscan VC 98 · Images of skin structure · Rz and Ra in µm 	BL, after 2 hours and 20 minutes after loading
Skin elasticity/deformability	
 · Cutometer MPA 580 (Courage& Khazaka, Germany) · Means of duplicate measurements per skin area in mm 	BL, after 2 hours and 20 minutes after loading
Skin surface temperature	
 · Measurement with Skin-Thermometer ST 500 · (Courage+Khazaka electronic GmbH) · Means of duplicate measurements per skin area in °C per skin area 	BL, after 2 hours and 20 minutes after loading
Epidermal and dermal hydration	
 · Measurement with MoistureMeterEpiD (Delfin Technologies) · Percentage of tissue water (0-100%) (0,5mm measurement depth) 	BL, after 2 hours and 20 minutes after loading
Epidermal/dermal characteristics (only for basic foam)	
 · OCT (Thorlabs, Lübeck, Germany), image processing and measurements according Trojahn et al. 2015 · Descriptive 	BL and after 2 hours
Skin thickness (only for basic foam)	
 · OCT (Thorlabs, Lübeck, Germany), image processing and measurements according Trojahn et al. 2015 · µm (metric) 	BL and after 2 hours

Table 2. Variables

Name	Method and metric	Time points
Age	Checking by looking at the ID card (metric)	Inclusion
Body temperature	Clinical thermometer in °C	BL, after two hours
Heart rate	Beats per minute (bpm)	BL, after two hours
Blood pressure	Millimeters of mercury (mmHg)	BL, after two hours
BMI (body height, weight)	kg/m ²	Inclusion
Phototype	Categories I, II, III	Inclusion

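### Section 4.4 provides no masked reading of stored Visioscan and OCT images, although its reason for not blinding does not reach work done on images afterwards

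*Combined protocol and SAP*

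**What the plan says.** Section 4.4 (Blinding) has two sentences. The first says that "study assistants and researchers will not be blinded" and gives the nature of the intervention as the reason. The second reads "The data manager and statistician will be blinded". No other role is masked, and no section mentions coded or masked reading.

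Table 1 in section 3.3 has nine outcome rows. Three come from images:

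- Skin roughness, listed as "Images of skin structure" from the Visioscan with the metric "Rz and Ra in µm", at baseline, after 2 hours and 20 minutes after loading. The row is not restricted to any surface.
- OCT epidermal and dermal characteristics, basic foam only, at baseline and after 2 hours. The metric is given only as descriptive.
- OCT thickness, in the row that begins "Skin thickness (only for basic foam", at the same two time points, in µm.

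Both OCT rows refer image processing and measurement to a cited publication. The sequence of measurements in section 3.2 likewise limits OCT to the foam mattress. No section says who processes the images, when, or with what labels visible.

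**The concern.** The reason given for leaving staff unmasked is that the mattress can be seen. That holds for anyone positioning the volunteer or taking a probe reading at the bedside. It does not hold for a person who later opens a stored image file, because surface and time point can be hidden there by relabelling.

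Section 2.1 sets an expectation: earlier work is said to show that prolonged loading changes skin structure and function, and a link between type of surface and skin response is called highly likely. A reader who shares that expectation and sees the label could shift whatever judgement the reading requires. For OCT the only contrast is before against after loading on one surface, so no comparator surface could reveal such a shift. For roughness the stake is objective 2 in section 2.2, the difference between surfaces.

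**Working it through.** **1. Does the stated reason cover each image outcome?**

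| Outcome (Table 1) | Surfaces | Contrast | Label that could sway a reader | Hidden by coding? |
|---|---|---|---|---|
| Roughness, Rz and Ra | all three | change over time, and between surfaces | surface, time point | yes |
| OCT characteristics, descriptive | foam only | baseline against 2 hours | time point | yes |
| OCT thickness, µm | foam only | baseline against 2 hours | time point | yes |

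Visit number must also be hidden for roughness, because with the randomized order it identifies the surface.

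**2. Which reader shift does harm?** Let b(j,t) be the mean shift a reader adds on surface j at time t.

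- OCT change on foam: bias = b(foam, 2 h) − b(foam, baseline).
- Roughness change compared between surfaces A and C: bias = [b(A, 2 h) − b(A, baseline)] − [b(C, 2 h) − b(C, baseline)].

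A shift common to all images cancels in both. A shift that depends on time point but is the same on every surface cancels in the second and remains in the first. Only a differential shift matters. If coding hides j and t, the reader's expectation cannot make b depend on them.

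**3. The plan's own figure.** Section 3.5 gives n = 15, SD 10 g/m²/h, power 0.8, alpha 0.05 and a detectable difference of about 8 g/m²/h in TEWL change. Taking the SD as that of the within-subject difference and a two-sided paired t-test (14 degrees of freedom, noncentral t), the detectable difference at power 0.80 is 7.78, and power at exactly 8 is 0.821. The figure reproduces after rounding. The present point does not depend on it, but it supports a paired t-test at n = 15 as an illustration.

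**4. Illustration for the numeric outcomes.** Suppose the true difference is zero and the differential reader shift is δ SDs of the paired difference. The noncentrality is δ√15, the critical value is t(0.975; 14) = 2.145, and the rejection probability is P(|T| > 2.145).

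| δ (assumed) | δ√15 | Rejection probability |
|---|---|---|
| 0 | 0 | 0.050 |
| 0.05 | 0.194 | 0.054 |
| 0.1 | 0.387 | 0.065 |
| 0.2 | 0.775 | 0.112 |
| 0.3 | 1.162 | 0.192 |
| 0.5 | 1.936 | 0.438 |

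The documents give no value for δ. The table does not apply to the descriptive OCT row, which has no numeric metric. Section 5.2 plans mainly descriptive analysis with comparisons for dependent samples and names no test, so the paired t-test is also an assumption.

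**The case against.** The strongest reply is that the plan may contain little reader judgement to bias. Rz and Ra are numeric parameters and may be computed by software. OCT thickness follows a published method that is not reproduced in the protocol. If those steps are automated, coding changes little. At shifts of 0.05 to 0.1 SD the false-positive chance barely moves. The study is exploratory with no primary outcome. OCT is not named in objective 1 and cannot serve objective 2, since only foam is imaged. All of this stands, and it limits the weight of the point.

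Three stronger readings are tempting, and the documents do not support them:

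- That unmasked researchers do process the images. This is a natural inference from section 4.4, but no reader is named. The defect is that the plan permits it.
- That knowing the mattress biases the OCT results. Every OCT image comes from foam, so only time point can act there.
- That the false-positive chance is inflated to a particular figure. The table rests wholly on assumed shifts.

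The reply does not remove the core. A descriptive OCT reading plainly involves judgement, any operator choice in roughness bears on the between-surface comparison, and the stated reason for not masking does not cover either.

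**Conclusion.** The point holds as a low-cost improvement, not as a flaw that undermines the trial. As written, section 4.4 allows avoidable reader bias in three of nine outcome rows. The risk is clearest for the descriptive OCT before-after reading. It is less certain for roughness and OCT thickness, where the degree of automation is not stated. The size of any bias is unknown. For numeric outcomes, an assumed differential shift of 0.1 SD would do little harm (about 7% instead of 5%), while 0.2 or 0.5 SD would give about 11% or 44%. These figures assume a two-sided paired t-test with n = 15 and no true difference.

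**What to change.** In section 4.4, keep bedside staff unmasked and add:

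- who processes the Visioscan and OCT images;
- that Visioscan files carry random codes hiding surface, visit and time point, and OCT files carry codes hiding time point;
- that the usual reader works only from coded files, and the key is released after the image values are locked.

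This has to be in place before reading starts, because a reader who has seen labelled images cannot be masked to them afterwards.

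The cost is file renaming, a code list and a short wait before processing. No extra reader, visit or measurement is needed. Two limits should be stated in the protocol: coding does not remove bias at image acquisition, and masking may be imperfect if the reader also took the images.

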5.1 Data collection and management

All data collectors will be trained in obtaining accurately the variables of interest (see 3.3).

Paper source data (SD) will be used to document all study variables of interest. The data manager creates an SPSS file and data of the SD are entered (single data entry). After data are entered, a random subset will be verified by an independent person (SD verification) who was not involved in the data entry so far.

5.2 Statistical methods

Depending on the level of measurement (nominal, ordinal, continuous) variables will be described using absolute and relative frequencies or arithmetic means, medians and spread parameters (minimum, maximum, interquartile ranges, standard deviations). Statistical analyses will be primarily descriptively including group comparisons for dependent samples.

6 Methods: monitoring

6.1 Data monitoring

Data monitoring is not planned.

6.2 Harms

Harms, like pain, persisting erythema for more than 30 minutes or possible irritant reactions, which occur immediately or after loading will be documented as an adverse event.

Within this trial the following definitions of adverse events will be used:

Device Deficiency (DD)

Inadequacy of a medical device with respect to its identity, quality, durability, reliability, safety or performance.

Note: Device Deficiencies include malfunctions, use errors, and inadequate labelling. All Device Deficiencies that could have led to a Serious Adverse Device Effect shall be reported in accordance with Serious Adverse Event reporting procedures.

Adverse Events (AE)

Any untoward medical occurrence, unintended disease or injury, or untoward clinical signs (including abnormal laboratory findings) in subjects, users or other persons, whether or not related to the investigational medical device.

Note: This definition includes events related to the investigational medical device or the comparator. This definition includes events related to the procedures involved. For users or other persons, this definition is restricted to events related to investigational medical devices.

Adverse Device Effect (ADE)

Adverse Event related to the use of an investigational medical device.

Note: This definition includes adverse events resulting from insufficient or inadequate instructions for use, deployment, installation, implantation, or operation, or any malfunction of the investigational medical device. This definition includes any event resulting from use error or from intentional misuse of the investigational medical device.

Serious Adverse Event (SAE)

Adverse Event that:

- i. leads to death;
- ii. leads to a serious deterioration in the health of the subject, that either resulted in:
 - a. a life-threatening illness or injury, or
 - b. a permanent impairment of a body structure or a body function; or
 - c. prolonged hospitalization; or,
 - d. medical or surgical intervention to prevent life-threatening illness or injury or permanent impairment to a body structure or a body function;

Serious Adverse Device Effect (SADE)

Adverse Device Effect that has resulted in any of the consequences characteristic of a Serious Adverse Event.

According to the Guidelines on Medical Devices (European Commission 2010) the above listed definitions only apply for non-CE marked devices and Conformité Européenne CE marketed devices outside the intended use. The support surfaces used in this study are already CE marketed and are used within the intended use. Therefore formal reporting modalities do not apply. However, (1) SAEs and (2) DD that might have led to a SAE will be reported not later than 2 calendar days to the manufacturer using the reporting form in Appendix 1.

7 Ethics and dissemination

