In recent years the concept of “microclimate” received increasing attention. It is defined as the temperature, humidity, and air-flow on and near to the skin surface. The parameters of skin temperature and humidity are closely related to functional and mechanical skin properties and to the susceptibility to PU development (Gefen 2011, NPUAP, EPUAP, PPPIA 2014). Therefore, many support surfaces try to influence the microclimate as well. A major methodological challenge in current PU research is the lack of outcomes to measure the effects of preventive approaches. PU incidence is clearly the clinical most relevant parameter. However, using this dichotomous outcome well conducted RCTs require hundreds of patients, long recruitment and follow-up periods, and are expensive. In addition, there is a debate whether the current definition of PU incidence in clinical trials is really the best choice (Kottner, Gefen 2012). Widely agreed upon Core Outcomes Sets (Clarke, Williamson 2015) have not been developed in PU research so far (Nixon 2015). Attempts have been made, to identify possible other parameters serving as predictors or biomarkers for PU risk and/or early tissue damage, e.g. skin temperature, shear wave velocity based on ultrasound elastography, epidermal cytokines, or serum myoglobin. It is well known, that skin function for instance in terms of transepidermal water loss (TEWL) is very sensitive marker of skin barrier changes. TEWL increases are usually associated with skin barrier impairments whereas TEWL decreases are associated with an intact or improved skin barrier (Rogiers et al. 2001). Using a standard hospital mattress, it was shown recently that this parameter shows a loading time depend increases in the lateral heel areas indicating subclinical skin damage (Kottner et al. 2015). Skin temperature and erythema increased as well; both being directly related to the risk of tissue damage. These functional parameters were also partly

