3.4 Participant timeline

Table 3. Participant timeline

	Inclusion	V1, V2, V3*				
		0 to 30 min (acclimatization)	Baseline measurements	2 hours (supine position)	Prone position	Prone position after 20 minutes
In-/exclusion criteria	x					
Signed Informed consent	x					
Demographics	x					
BMI	x					
Physical examination	x					
Marking of measurement areas	x					
Randomization	x					
Heart rate	x					
Blood pressure	x					
Body temperature	x					
Skin measurements at sternal skin			x	x		
Skin measurements at right heel and sacral skin			x		x	x
Adverse events monitoring		x	x	x	x	x

*same protocol on V1, V2, V3 (only change of support surface depending on randomized order), V3: end of study

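### Erythema lasting more than 30 minutes is listed as an adverse event, but the last scheduled skin and adverse-event check is at 20 minutes after loading

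*Combined protocol and SAP*

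**What the plan says.** Section 6.2 gives examples of harms to be recorded as adverse events, and only one of them carries a duration: "Harms, like pain, persisting erythema for more than 30 minutes or possible irritant reactions, which occur immediately or after loading will be documented". The general definition that follows in 6.2 is wider. It covers any untoward sign and sets no time limit.

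The schedule appears in three places:

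- Section 3.2, after the post-load measurements at heel and sacrum: "The measurements will be repeated after 20 min to observe the adjustments after offloading".
- Section 3.3, Table 1, time points for erythema: "BL, after 2 hours and 20 minutes after loading".
- Section 3.4, Table 3: the last column is "Prone position after 20 minutes". It is the last one ticked both for heel and sacral measurements and for adverse-event monitoring. The footnote adds "V3: end of study".

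No section schedules a skin look, a call or any other contact later than this within a visit, or after the third visit.

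**The concern.** Some redness after two hours of loading is expected. Of the earlier study on a standard hospital mattress, section 2.1 says: "Skin temperature and erythema increased as well; both being directly related to the risk of tissue damage". If redness as such is expected, its duration is what marks it as a harm, and 30 minutes is the only duration the plan gives. A criterion of this kind can be applied only by looking after the limit has passed.

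For a woman still red at 20 minutes, whether the criterion is met would depend on how long the last round happens to take, or on informal observation by staff who are not blinded (section 4.4). A report of no persisting erythema could mean that it did not occur or that nobody had to look. The next visit's baseline does not settle this. It would show redness that never cleared, but not redness that lasted, say, 45 minutes, and after the third visit there is no later baseline.

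**Working it through.** **Inputs from the protocol**

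- Adverse-event limit: more than 30 minutes (6.2).
- Last scheduled round: starts 20 minutes after loading (Table 1), so the clock is taken to start when the participant turns prone.
- Measurements in that round: seven (3.2, steps 1 to 7). OCT is excluded because Table 1 has it only at baseline and after two hours.
- Readings: "Measurements will be performed two times per measurement area".
- Sites: two, right heel and sacrum.
- Visit: "every subject will have at least three visits in the study center of approximately 4 hours", with 30 minutes of acclimatization and 120 minutes of loading.

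The protocol gives no time per reading or per site. I write x for minutes per site, **an assumption**, and show x = 3, 5, 8 and 10. The post-load round at two sites must finish before the 20-minute round starts, so 2x ≤ 20 and x ≤ 10.

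**Step 1: the gap.** 30 − 20 = 10 minutes between the start of the last scheduled round and the limit.

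**Step 2: does the last round reach past 30 minutes?** Readings = 7 × 2 × 2 = 28. The 10 minutes are 600 s, and 600 / 28 = 21.4 s per reading. The round passes 30 minutes only if readings average more than that, handling included. The cap x = 10 corresponds to 1200 / 28 = 42.9 s per reading, so both outcomes are possible. The round ends at 20 + 2x:

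| x (min per site, assumed) | 3 | 5 | 8 | 10 |
|---|---|---|---|---|
| Last round ends (min after turning prone) | 26 | 30 | 36 | 40 |

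**Step 3: when is erythema itself last measured?** It is step 4 of 7. Take the slowest case, x = 10, with equal time per measurement (a further assumption). If the sites are done one after the other, the first site's erythema reading starts at 20 + (3/7) × 10 = 24.3 minutes. If each device goes to both sites in turn, it starts at 20 + (3/7) × 20 = 28.6 minutes. Even then, the last scheduled erythema reading at one site begins before the limit. The reading is in arbitrary units, and the plan sets no value that counts as still red.

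**Step 4: what would a look at 35 minutes cost?** Extra stay per visit = max(0, 35 − (20 + 2x)) = max(0, 15 − 2x), which never exceeds 15. Visit length with the look, counting both sternal rounds on top of the two hours and leaving out OCT on the foam visit = 30 + 2x + 120 + 2x + max(35, 20 + 2x).

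| x (min per site, assumed) | 3 | 5 | 8 | 10 |
|---|---|---|---|---|
| Extra stay per visit (min) | 9 | 5 | 0 | 0 |
| Extra stay over three visits (min) | 27 | 15 | 0 | 0 |
| Visit length with the look (min) | 197 | 205 | 218 | 230 |

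All four totals are within the planned visit of about 240 minutes.

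**The case against.** The strongest reply is that the skin will in practice be seen after 30 minutes.

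- **The last column of Table 3 can be read as a phase.** It has a start and no stated end, so adverse-event monitoring could be taken to continue from 20 minutes onward.
- **The clock in 3.2 is loose.** The 20 minutes could run from the end of the first post-load round. The last round would then start at 20 + 2x and end at 20 + 4x, that is 32, 40, 52 or 60 minutes for the four values of x, past the limit every time.
- **The participant is probably still on site.** On the model above she turns prone at 150 + 4x minutes, so the 30-minute mark falls at 192, 200, 212 or 220 minutes. That leaves 48, 40, 28 or 20 minutes of a 240-minute visit, before any OCT.
- **The list in 6.2 is illustrative.** The general definition has no time limit, so trained staff may record redness at any time, and a source document not shown here might prompt for it.
- **Little hangs on it.** The participants are healthy volunteers with two hours of exposure on CE-marked surfaces used as intended, and no decision rule uses this event.

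Much of this is fair, and it limits the weight of the point. It does not remove it. Table 1 ties the 20 minutes to loading, which favours the reading used here. Being in the building, or at the skin for another measurement, is not a required record of whether redness persists. The wider definition lets staff record redness early, but that bypasses the duration criterion and does not apply it.

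**Conclusion.** The concern holds, as a minor point of safety ascertainment. Followed as written, the plan cannot reliably apply its own criterion of more than 30 minutes, because the last required observation starts 10 minutes before the limit. Whether staff are still at the skin after 30 minutes depends on an unstated reading time, with break-even at about 21 seconds per reading. This rests on Table 1's clock starting at the end of loading; the per-site times are assumptions.

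The erythema outcome and the TEWL analysis are unaffected, and the plan makes no comparison of harms between mattresses. The protocol gives no harm rate, so the number of missed or misclassified events cannot be derived.

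**What to change.** 1. Add one timed yes/no visual check of heel and sacrum just after 30 minutes from turning prone, for example at 35 minutes and before the participant leaves, on all three mattresses, with its own column in Table 3. If the last round is still running, do the look within it; it does not touch the skin. If a site is still red, record the adverse event under 6.2 and note when it resolves.
2. State in 3.2 that the 20-minute measurement and this check are both timed from turning prone at the end of loading.
3. Optional: at the baseline of the second and third visits, confirm that any such event has resolved before loading again.

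The cost is one look per visit, one table column and two sentences notified to the ethics committee. The only downside is a slightly longer stay for participants whose measurements finish early.
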